4.1. Study Design

This is a Phase 2, randomized, double-blind, placebo-controlled, dose range finding study in subjects who have DPN. The study will enroll approximately 24 subjects. Subjects will be randomized to receive one of 3 treatments: PDA-002 (3×10^6 cells), PDA-002 (30×10^6 cells), or placebo (vehicle control) in a 1:1:1 randomization approach. Investigational product or placebo will be administered monthly (3 administrations total on Study Days 1, 29, and 57). Subjects will be treated and evaluated as indicated in the Table of Events (Table 1).

Subjects will undergo a Screening Period (up to 28 days in duration) to determine study eligibility and baseline levels of signs and symptoms of DPN will be established. Subjects will then enter a Treatment Period (6 months in duration). During the Treatment Period, subjects will be evaluated on an ongoing basis (at 8 scheduled study visits). Subjects will receive IM injections of IP on Study Days 1, 29, and 57 as fifteen 0.30 mL injections (below the knee and above the ankle) in one lower extremity in a blinded manner. After completing the Treatment Period, subjects will enter the Follow-up Period where they will continue to be evaluated at scheduled study visits over the subsequent months.

An analysis of all study data will occur after the last subject has completed Visit 9 (Month 6) and after the last scheduled study visit. Analyses to be performed can be found in the Statistical Analysis Plan.

The study will be subject to oversight by an independent Data Monitoring Committee (DMC). The DMC will review unblinded efficacy and safety data on an ongoing basis (both scheduled and ad hoc [if needed]) as outlined in the DMC Charter.

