The doses selected for this study are based upon the effective doses adjusted for body weight that were administered in the previously described hind limb ischemia (HLI) animal models, as well as the dosing in the Phase 1 study PDA-002-DFU-001. Data on the first 3 dose cohorts of the Phase 1 study in which subjects were administered 3 x 10^6 cells, 10×10^6 cells and 30×10^6 cells on Days 1 and 8 demonstrated that the doses were well tolerated with no reported dose limiting toxicity (DLT). To date based upon the observed safety profile from the Phase 1 study, no new risks have been identified for PDA-002 that would preclude dosing in the Phase 2 studies.

For this study, subjects will be randomized to receive PDA-002 or placebo in one lower extremity in a blinded manner. Although PDA-002 is being administered IM, it is unclear if the therapeutic effect is localized to the area of injection or systemic. In pre-clinical HLI studies, the therapeutic effect of PDA-002 was similar in animals administrated the IM and intravenous (IV) formulation. The mechanism of action of PDA-002 is due to a modulation of the immune system from a pro inflammatory to anti-inflammatory state that facilitates angiogenesis both in the area directly in contact with PDA-002 along with other areas that may be affected by inflammation and ischemia. Since DPN causes a symmetrical dysfunction to the nerves of the lower extremities, assessments of nerve function as well as changes in neurologic signs will be assessed in both legs in order to determine if the therapeutic effect of PDA-002 is local vs. systemic.

The dosing schedule of PDA-002 in this study will be 3 repeated monthly administrations. The schedule is based on the safety of 3 repeat IM doses of PDA-002 demonstrated in animal studies. Please refer to the Investigator's Brochure for detailed information concerning the available pharmacology, toxicology, drug metabolism, clinical studies, and AE profile of PDA-002.

One additional design feature of this study is that while PDA-002 is injected into one leg, both legs are checked for changes in neuropathy signs and symptoms. This will enable determining if the effects of PDA-002 on DPN are limited to the area in which the cells are injected, or the effect is systemic.

Figure 1: Overall Study Design

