8.2. Treatment Administration and Schedule

Investigational product (IP) will be administered on Study Days 1, 29 and 57. Thawing of the IP should not begin until it is confirmed that the subject meets the inclusion/exclusion criteria. Investigational product thawing will be performed by qualified site personnel according to the instructions in Appendix E. Three 3 mL syringes will each be filled with 1.5 mL of IP, and then capped. Syringes will be masked to preserve blinding, and transferred to the personnel administering the injections.

Subjects will receive IP administered as fifteen 0.30 mL injections (approximately 4.5 mL total) in one leg. The target region is suggested to be below the knee and above the ankle. Injections are suggested to be at least 1 cm apart horizontally and laterally and at a depth of approximately 1 to 4 cm. It is suggested that they be administered in a pattern of 3 x 5 injections around the leg, and injections should not be near a blood vessel. The administrator will be blinded to treatment.

PDA-002 is not intended for intravenous administration. When the injection is given, the syringe should be aspirated to avoid inadvertent venous administration. If any blood is aspirated into the syringe, the needle is to be pulled out a little, and the syringe re-aspirated. If no blood is seen, the IP may be injected.

Vital signs (including heart rate, respiration, blood pressure, body temperature) will be monitored prior to starting the injections and at 1 and 2 hours (\pm 15 minutes) after completion of

the injections. Blood samples for tryptase and histamine, coagulation assessments, and exploratory biomarkers will be collected as indicated in the Table of Events (Table 1).

The investigational centers must also offer appropriate supplemental services that support clinical care to ensure that the protocol specified IP administration and monitoring will be followed.

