Administration Instructions. Under aseptic conditions, PDA-002 or placebo will be injected IM at 15 sites in one limb on Study Days 1, 29, and 57. The injection volume will be 0.30 mL per injection site. A 3.0 mL syringe with a 20 to 22-gauge 1.5-inch long needle will be used to inject the IP. The target region is suggested to be below the knee and above the ankle. Injections are suggested to be at least 1 cm apart horizontally and laterally and at a depth of approximately 1 to 4 cm. It is suggested that they be administered in a pattern of 3 x 5 injections around the leg, and injections should not be near a blood vessel. The administrator and the subject will be blinded to treatment.

A diagram of the recommended injection grid and anatomical site selection is provided in Appendix E.

The entire thawed IP must be administered within 4 hours of thaw start time and within 1 hour of the syringe fill time. In the event that it becomes medically necessary to stop the injections, the stop time of the injections as well as the time the injections are resumed must be noted in the eCRF and in the source documents. If less than the total injection volume is administered, the volume injected should be recorded and the sponsor should be notified.

Note: For this study, all \geq Grade 3 allergic reactions associated with the use of IP must be reported to Celgene Cellular Therapeutics as an SAE within 24 hours of the investigator's knowledge of the event.

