10.6. Efficacy Analysis

The planned analyses will be fully described in a comprehensive SAP.

The primary efficacy analysis will be an evaluation of change from baseline in ENFD at 6 months following treatment with either dose of PDA-002 or placebo. Results will be used to assess the proof of concept for further study of PDA-002 in subjects with DPN. The analyses will also take into account the possible inter-subject variability of measurements evaluated in both the treated leg (with active or placebo) and the other leg that received placebo.

Changes in the various exploratory efficacy endpoints including within subject differences between left and right leg measurements will be evaluated using descriptive statistics.

In general, exploratory endpoints that are categorical will be examined using descriptive summaries such as counts and percentages, whereas exploratory endpoints that are continuous will be examined using means, standard deviations and medians. The results of the exploratory analyses will allow for better definition of the clinical efficacy endpoints.

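### Section 10.6 calls the second leg a placebo leg, but it is never injected; the leg contrast should be injected versus uninjected and compared between randomised arms

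*Combined protocol and SAP*

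**What the plan says.** Section 10.6 (Efficacy Analysis) makes change from baseline in ENFD at 6 months the primary analysis. It adds that the analyses will allow for variability of measurements in "the treated leg (with active or placebo) and the other leg that received placebo". For the exploratory endpoints it plans descriptive within-subject differences between left and right legs. The Efficacy and Safety Analyses paragraph of the Protocol Summary also frames the systemic-or-local question in left/right terms.

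The administration text is consistent and different:
- Section 4.1: "fifteen 0.30 mL injections (below the knee and above the ankle) in one lower extremity in a blinded manner".
- Section 4.2: "subjects will be randomized to receive PDA-002 or placebo in one lower extremity in a blinded manner".
- Section 8.2: "Subjects will receive IP administered as fifteen 0.30 mL injections (approximately 4.5 mL total) in one leg", and in its administration instructions "PDA-002 or placebo will be injected IM at 15 sites in one limb on Study Days 1, 29, and 57".
- Protocol Summary, Study Treatments: the same leg is used at each dosing, chosen by a score rule (investigator's choice if tied), and placebo subjects are treated in the same manner.

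Section 4.2 explains why both legs are measured: "it is unclear if the therapeutic effect is localized to the area of injection or systemic", and "while PDA-002 is injected into one leg, both legs are checked for changes in neuropathy signs and symptoms". Sections 6.1 and 6.4 provide a distal-leg biopsy from each leg.

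**The concern.** The sentence in 10.6 gives the second leg a control status that it does not have. In a placebo subject that leg is uninjected. In a PDA-002 subject it is uninjected and, by the reasoning of Section 4.2, may still respond to treatment. An analyst who takes the label at face value could treat a PDA-002 subject's uninjected leg as a placebo observation.

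Two things are left unsettled. Section 10.6 does not say which leg's ENFD is primary, although both are biopsied. It also does not state a leg contrast that could answer the local-versus-systemic question. A left/right difference does not track treatment. A leg difference within treated subjects alone can miss a systemic effect, or credit the cells with an effect of the needle or vehicle. At stake is the interpretation of the two-leg feature, in a study meant to supply estimates for sizing the next one.

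**Working it through.** **1. The plan's own power figures (Section 10.3).** Inputs: change 3.07 − 1.56 = 1.51 fibers/mm; SD of change 1.5; two-sided 0.05; 16 active and 8 placebo subjects; no change on placebo. The method is the noncentral t.
- Active change from baseline, n = 16: noncentrality 1.51/1.5 × √16 = 4.03 on 15 df, power 96.4% (stated 96%).
- Active versus placebo, 16 v 8: noncentrality 1.51/(1.5 × √(1/16 + 1/8)) = 1.51/0.650 = 2.32 on 22 df, power 60.4% (stated 60%).

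Both reproduce. Neither uses a leg contrast, so correcting the phrase changes neither.

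**2. The left/right difference.** Suppose the effect is purely local (1.51) and a proportion p of PDA-002 subjects are injected on the left. The mean left-minus-right difference is p × 1.51 − (1 − p) × 1.51 = 1.51 × (2p − 1). The protocol does not give p, which depends on the score rule. The result is 0 at p = 0.5, 0.302 at p = 0.6, 1.208 at p = 0.9 and 1.51 at p = 1.

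**3. Injected versus uninjected legs.** Let L be a local cell effect, S a systemic effect and V a needle or vehicle effect in the injected leg. Mean changes are:
- PDA-002 subjects: injected leg L + S + V, uninjected leg S.
- Placebo subjects: injected leg V, uninjected leg 0.

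Each effect in turn is set to 1.51 and the others to 0. For L and S this is the protocol's planning effect. For V it is an illustrative assumption, because the documents give no needle or vehicle effect.

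| Contrast | Systemic only | Local only | Needle/vehicle only |
|---|---|---|---|
| Injected − uninjected, PDA-002 subjects only: L + V | 0 | 1.51 | 1.51 |
| The same difference, PDA-002 minus placebo subjects: L | 0 | 1.51 | 0 |
| Uninjected leg, PDA-002 minus placebo subjects: S | 1.51 | 0 | 0 |
| Injected leg, PDA-002 minus placebo subjects: L + S | 1.51 | 1.51 | 0 |

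The first row shows nothing under a systemic effect and cannot tell columns two and three apart. The next two rows, both between randomised arms, separate all three explanations. The last row captures the total cell effect whether it is local or systemic.

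**4. Precision of the between-arm leg contrast.** With between-leg correlation ρ of the changes, the SD of a subject's leg difference is 1.5 × √(2(1 − ρ)). The between-arm standard error is that SD × √(1/16 + 1/8). The documents do not give ρ, so a range is shown for a local effect of 1.51.

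| ρ (assumed) | SD of leg difference | Standard error, 16 v 8 | Power |
|---|---|---|---|
| 0 | 2.121 | 0.919 | 35% |
| 0.5 | 1.500 | 0.650 | 60% |
| 0.7 | 1.162 | 0.503 | 82% |
| 0.8 | 0.949 | 0.411 | 94% |

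Against the one-arm leg difference (standard error SD/√16), the ratio of standard errors is √((1/16 + 1/8)/(1/16)) = √3 = 1.73 at any ρ.

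**The case against.** The strongest reply is that this is a slip of wording. Section 10.6 does not say that the second leg serves as a control, and it states no rule for pooling legs. The Protocol Summary describes the leg assessment without any placebo label and calls it descriptive. The primary objective (Section 2.1) compares PDA-002 with placebo subjects, and the 60% power is for that comparison. Local versus systemic effect is exploratory (Section 2.3). Sections 10.1 and 10.6 defer detail to a separate SAP, which is not in the text reviewed and may define the contrast. Nothing in the documents suggests that needling or vehicle changes ENFD: Appendix E places injections 1 to 4 cm deep in calf muscle, while Section 6.1 takes the skin biopsy about 10 cm above the lateral malleolus.

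Most of this stands, and it limits the point. Two stronger readings are tempting, and the documents support neither:
- A reader might infer that the leg contrast has no placebo control at all. It has one: placebo subjects receive vehicle in one leg under the same selection rule, and both their legs are biopsied.
- A reader might infer that uninjected legs of PDA-002 subjects will be pooled with placebo legs, diluting the primary effect and its power. No such pooling is stated, so no loss of effect or power can be attributed to the plan.

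What the reply does not remove is the false description in the primary-analysis paragraph, the silence on which leg is primary, and a stated leg contrast that cannot do its job. A sound SAP would still contradict the protocol's description of the second leg.

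**Conclusion.** The point holds in this form. Section 10.6 contradicts the Protocol Summary and Sections 4.1, 4.2 and 8.2 about what the second leg receives. The stated left/right difference does not follow the injected leg, and a leg difference within PDA-002 subjects alone would not be enough either. On the protocol's scale, that one-arm difference is 0 for a wholly systemic effect of 1.51. It takes the same value for a local effect as for an equal needle or vehicle effect.

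These values assume additive effects and no change in the placebo arm's uninjected leg; the size of the needle or vehicle effect is illustrative, and whether one exists is unknown. The randomised comparison between arms and the 96% and 60% power figures are untouched. The contradiction is certain. Its practical effect depends on the separate SAP. It should be fixed, but it is not critical, because the question it affects is exploratory and descriptive.

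**What to change.** Reconcile 10.6 with the administration sections and carry the same text into the SAP:
1. Describe the second leg as the other leg, which receives no injection.
2. Define legs as injected or uninjected, in place of left or right, in 10.6 and in the Protocol Summary.
3. Name the primary variable: 6-month ENFD change in the injected leg, PDA-002 versus placebo subjects.
4. Report two further contrasts descriptively, with intervals: (a) change in the uninjected leg, PDA-002 versus placebo subjects, for a systemic effect; (b) injected-minus-uninjected change, PDA-002 versus placebo subjects, for a local effect.
5. State that uninjected legs of PDA-002 subjects are never counted as placebo observations.

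Settle this before the sponsor is unblinded after Month 6 (Section 8.7), so that the contrast is not chosen after seeing the results. The cost is wording only: both legs are already biopsied in every arm, and no dosing text changes. The statistical price is a wider interval for the local estimate, with a standard error 1.73 times that of a one-arm leg difference. That is acceptable for a descriptive contrast that removes the needle or vehicle explanation.

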The study population includes subjects with Diabetic Peripheral Neuropathy due to Type 2 diabetes mellitus (DM) as defined by the ADA or WHO criteria (Appendix A).

Length of Study

Subjects are expected to participate in the study from screening (Day 28) to 1 year after the -last IP injection.

Subjects will undergo a Screening Period of up to 28 days. During the Screening Period eligibility will be confirmed and baseline assessments will be performed. Subjects will then enter a 6 month Treatment Period consisting of 8 study visits. During the Treatment Period, IP will be administered on Study Days 1, 29, and 57, and efficacy and safety evaluations will be performed as outlined in the Table of Events (Table 1). Subjects will then enter a Follow-up Period. The Follow up Period will consist of bi-monthly study visits to continue to assess safety and longer-term efficacy.

End of Trial

The End of Trial is defined as either the date of the last visit of the last subject to complete the post-treatment follow-up, or the date of receipt of the last data point from the last subject that is required for primary, secondary and/or exploratory analysis, as prespecified in the protocol, whichever is the later date.

Study Treatments

Subjects will be randomized 1:1:1 to receive one of the following dose levels of IP:

- PDA-002 Dose Level 1: 3 x 10⁶ PDA-002 cells administered IM on Study Days 1, 29, and 57.*
- PDA-002 Dose Level 2: 30 x 10⁶ PDA-002 cells administered IM on Study Days 1, 29, and 57.*
- Placebo (vehicle control) subjects will receive placebo (vehicle control) administered in the same manner and at the same time points as the PDA-002 dosing groups.

*Subjects will be dosed in the same leg. The leg of injection will be the leg with the lowest combined qualifying NTSS-6 and UENS and NIS-LL score. In the case of a subject with an equal score for both legs, the choice of the leg to inject is at the discretion of the investigator.

PDA-002 and placebo (vehicle control) units will be shipped to the study sites as cryopreserved units and will be thawed and filled into syringes prior to IM injection.

Overview of Key Efficacy Assessments

The following efficacy assessments will be performed as outlined in the Table of Events (Table 1).

The primary efficacy assessment is the evaluation of change from baseline in Epidermal Nerve Fiber Density (ENFD) at 6 months.

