Based upon a previous study (Jacobs, 2011), the mean ENFD was 1.56 fibers/mm at baseline and 3.07 fibers/mm after 6 months of treatment with a standard deviation of 1.5 fibers/mm for the mean increase. Assuming the same treatment effect is observed from baseline, the sample size of

16 subjects actively on therapy resulting from combining the 2 active arms has a 96% power to detect a similar mean change at 6 months from baseline, with a two-sided test and a Type I error rate set at 0.05. Assuming the subjects treated with placebo would not have a change from baseline, the study has 60% power to detect similar differences between placebo and active therapy with PDA-002, with a two-sided test and a Type I error rate set at 0.05.

Efficacy and Safety Analyses

The planned efficacy and safety analyses will be fully described in a comprehensive SAP.

The efficacy analyses will also include a descriptive assessment of the exploratory objective to evaluate whether the treatment effect of PDA-002 is systemic or local. This will be done by taking into account the intersubject variability between measurements taken from the left and the right leg.

TABLE OF CONTENTS

TITLE H	PAGE	1
PROTO	COL SUMMARY	5
1.	INTRODUCTION	
2.	STUDY OBJECTIVES	
2.1.	Primary Objective	
2.2.	Secondary Objective	
2.3.	Exploratory Objectives	
3.	STUDY ENDPOINTS	
3.1.	Primary Endpoint	
3.2.	Secondary Endpoint	
3.3.	Exploratory Endpoints	
4.	OVERALL STUDY DESIGN	
4.1.	Study Design	
4.2.	Study Design Rationale	
4.3.	Study Duration	
4.4.	End of Trial	
5.	TABLE OF EVENTS	
6.	PROCEDURES	
6.1.	Study Entry/Screening Period (Visit 1)	
6.2.	Treatment Period (Visit 2 through Visit 9)	
6.3.	Follow-Up Period	
6.4.	Efficacy Procedures	
6.5.	Safety	
6.5.1.	External Data Monitoring Committee	
7.	STUDY POPULATION	
7.1.	Number of Subjects and Sites	
7.2.	Inclusion Criteria	
7.3.	Exclusion Criteria	
8.	DESCRIPTION OF STUDY TREATMENTS	
8.1.	Description of Investigational Product	
8.2.	Treatment Administration and Schedule	

PDA-002 Protocol CCT-PDA-002-DPN-001

821	Discontinuation	38
822	Overdose	
8.2.2.	Method of Treatment Assignment	
8.J. 8.4	Packaging and Labeling	39
8.5	Investigational Product Accountability and Disposal	39
8.6	Investigational Product Compliance	40
8.0. 8.7	Blinding	
0.7.	CONCOMITANT MEDICATIONS AND PROCEDURES	
9. Q 1	Permitted Concomitant Medications and Procedures	
9.1. 9.2	Prohibited Concomitant Medications and Procedures	
0.2	Required Concomitant Medications and Procedures	

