2.3. Exploratory Objectives

The key exploratory objectives of the study are to assess any potential treatment effects of IM administration of 2 different doses of PDA-002 versus placebo in subjects with DPN as measured by changes from baseline in:

- Epidermal nerve histology at 3 months
- Lower limb microvascular oxygenation
- Vascular reactivity
- DPN signs and symptoms
- Motor and sensory nerve conduction and autonomic function
- Health-related quality of life measures
- Vascular, immune, and/or neural and laboratory parameters
- Assessment of the systemic versus local efficacy of PDA-002

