3.3. Exploratory Endpoints

Exploratory endpoints of the study include measuring changes from baseline in:

- ENFD at 3 months
- Hyperspectral Imaging (HSI) to evaluate lower limb microvasculature oxygenation
- Vascular Reactivity by Laser Doppler Iontophoresis and Nerve Axon Reflex measurements
- Signs/symptoms of DPN as assessed by the 6-item Neuropathy Total Symptom Score (NTSS-6)
- Signs/symptoms of DPN as assessed by the Neurological Impairment Score of the Lower Limb (NIS-LL)
- Signs/symptoms of DPN as assessed by the Utah Early Neuropathy Scale (UENS)
- Motor and sensory nerve conduction and autonomic function as evaluated by electrophysiologic nerve conduction studies
- Quantitative Sudomotor Axon Reflex Testing (QSART)
- Health-Related quality of life (QOL) as measured by the Norfolk QOL-DN
- Vascular, immune, and/or neuronal and laboratory parameters measured in blood and/or epidermal tissues or other biological samples as appropriate
- Patient Global Impression of Change in Neuropathy (PGICN).

4. **OVERALL STUDY DESIGN**

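### The exploratory leg comparison is worded as left versus right, but the injected leg is chosen subject by subject; it should be worded as treated leg versus other leg

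*Combined protocol and SAP*

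**What the plan says.** **Objective.** Section 2.3 lists "Assessment of the systemic versus local efficacy of PDA-002" among the exploratory objectives, which are framed against placebo. Section 4.2 gives the reason for examining both legs: to learn whether effects are "limited to the area in which the cells are injected, or the effect is systemic".

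**Choice of leg.** Protocol Summary, Study Treatments: "Subjects will be dosed in the same leg", and "The leg of injection will be the leg with the lowest combined qualifying NTSS-6 and UENS and NIS-LL score". If the legs score equally, "the choice of the leg to inject is at the discretion of the investigator". Sections 4.1 and 8.2 describe injections into one leg only.

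**Analysis.** Section 10.6 states that, for the exploratory endpoints, "within subject differences between left and right leg measurements will be evaluated using descriptive statistics", with means, standard deviations and medians for continuous measures. The Summary (Efficacy and Safety Analyses) says of the systemic-or-local assessment: "This will be done by taking into account the intersubject variability between measurements taken from the left and the right leg". The preceding paragraph of 10.6, on the primary analysis, speaks instead of the treated leg and the other leg, and describes the other leg as having been given placebo.

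**Measures taken in both legs (section 6.4).** ENFD from biopsies on both sides (including "ENFD at 3 months", section 3.3), nerve conduction, and, at sites where they are available, hyperspectral imaging (HSI) and the lower-limb vascular reactivity measures.

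**The concern.** The scientific contrast is injected leg against non-injected leg. Because the injected leg is picked per subject, left is the injected side for some subjects and the non-injected side for others. Averaging left minus right over subjects then lets a local effect enter with a plus sign in some and a minus sign in others, so it cancels in part or in full. A programmer working from the protocol text alone would summarise the wrong difference.

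At stake is one listed exploratory objective, and the use that 10.6 makes of the exploratory results, namely to sharpen the clinical efficacy endpoints. A local effect could be understated or taken for a systemic one.

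Two wording problems in the same text affect how any leg contrast is read. The reference in 10.6 to placebo in the other leg conflicts with the one-leg injection in 4.1 and 8.2. The Summary and 10.6 also use an inter-subject term beside a comparison made within subjects.

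**Working it through.** **The plan's own figures.** Section 10.3 gives 96% power for the mean change in 16 active subjects and 60% for active versus placebo. With a difference of 3.07 − 1.56 = 1.51 fibers/mm, SD 1.5, two-sided 0.05 and the noncentral t distribution, these come out at 96.4% (one sample, n = 16) and 60.4% (16 versus 8). They do not depend on how legs are labelled and are not in dispute. The plan gives no figure for the leg comparison.

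**Signed reading.** Let δ be a purely local effect and q the share of subjects injected on the left (not in the documents).

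- Treated minus other: expected mean = δ, whatever the side.
- Left minus right: expected mean = qδ − (1 − q)δ = (2q − 1)δ, so the share shown is |2q − 1|.

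The share needs no SD and no effect size. The fibers/mm column is an ENFD illustration. It assumes δ = 1.51 and a per-leg SD of change of 1.5, both borrowed from the overall 6-month figures for another treatment in 10.3.

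| Left:right, 16 active | q | Share of local effect shown | Mean L − R if δ = 1.51 |
|---|---|---|---|
| 8:8 | 0.5 | 0% | 0 |
| 9:7 | 0.5625 | 12.5% | 0.19 |
| 10:6 | 0.625 | 25% | 0.38 |
| 12:4 | 0.75 | 50% | 0.76 |

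In one arm of 8 the share is 0% at 4:4, 25% at 5:3, 50% at 6:2 and 75% at 7:1. For HSI and vascular reactivity the relevant split is that of the subjects actually measured, who may be fewer. At an even split, a purely local and a purely systemic effect both give an expected mean of zero, so the mean cannot separate them.

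**Spread.** With r the correlation between the two legs' changes, SD_D = 1.5 × √(2(1 − r)), and Var(L − R) = SD_D² + 4q(1 − q)δ². At an assumed r = 0.5:

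- Treated minus other: SD = 1.50.
- Left minus right, 8:8: √(2.25 + 2.28) = 2.13.
- Left minus right, 10:6: √(2.25 + 2.14) = 2.09.
- Left minus right, 12:4: √(2.25 + 1.71) = 1.99.

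**Unsigned reading.** The plan does not state a sign, so absolute differences are possible. Under the same assumptions (r = 0.5), the mean absolute difference (folded normal) is 1.20 with no effect and 1.76 with δ = 1.51. The gap of 0.56 is 37% of δ (27% at r = 0, 46% at r = 0.7), and improvement cannot be told from worsening. Dropping the sign therefore does not repair the wording.

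**Precision of the corrected contrasts (ENFD).** The 95% CI half-width is t(0.975, n1 + n2 − 2) × SD × √(1/n1 + 1/n2). The SD is 1.5 for the other-leg change (systemic) and SD_D for the leg difference (local).

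| Comparison | Systemic | Local, r = 0 | r = 0.3 | r = 0.5 | r = 0.7 |
|---|---|---|---|---|---|
| 16 active vs 8 placebo | 1.35 | 1.90 | 1.59 | 1.35 | 1.04 |
| 8 (one dose) vs 8 placebo | 1.61 | 2.27 | 1.90 | 1.61 | 1.25 |

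**The case against.** The strongest reply is that this is loose wording and not a fixed analysis. Sections 10.1 and 10.6 defer the detail to a separate SAP. Neither 10.6 nor the Summary defines an estimator or a sign, and the sentence in 10.6 does not itself mention systemic versus local; only the Summary makes that link. With treated leg and other leg used one paragraph earlier, and the purpose stated in 4.2, left and right may be shorthand for both legs. The attenuation figures also depend on a side split that nobody has stated.

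Most of this stands, and it limits the weight of the point. It does not remove it. The treated/other wording belongs to the primary-analysis paragraph and does not govern the exploratory sentence. The only axis the protocol states for the exploratory comparison is the wrong one, and no supplied text recodes side to injected leg.

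A reader might infer three stronger things that the documents do not support:

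- **That the trial will miss a local effect.** This follows only if the SAP takes a signed left-minus-right mean without recoding, which cannot be seen.
- **That information is lost or the primary test is compromised.** If the injected side is recorded, the legs can be recoded at analysis. The primary paragraph of 10.6 already uses treated and other leg.
- **That the inter-subject wording is a proven error.** It could mean ordinary between-subject variability in leg measurements; it needs clarifying.

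**Conclusion.** The concern holds as a minor correction to an exploratory, descriptive analysis. The protocol states the leg comparison on an axis that does not match its own question. Read literally and with a sign, the summary shows between none of a purely local effect (even split) and all of it (every subject injected on the same side). That result rests only on q, which is unknown. The ENFD figures rest in addition on a borrowed effect and SD and an assumed leg correlation, and are illustrations.

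Even the corrected contrasts are imprecise. For 16 versus 8, the half-widths of about 1.0 to 1.9 fibers/mm are of the same order as the assumed effect of 1.51, so the objective may stay unresolved with 24 subjects.

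**What to change.** 1. In section 10.6 and the Summary, replace left and right with treated leg and other leg.
2. For every measure taken in both legs (ENFD, nerve conduction and, where available, HSI and lower-limb vascular reactivity), summarise by arm (a) change in the treated leg minus change in the other leg, as the local contrast, and (b) change in the other leg, as the systemic contrast. Describe each for PDA-002 versus placebo with confidence intervals. The placebo comparison matters because the leg is selected on baseline score, so regression to the mean alone could separate the legs.
3. Confirm that the injected side is an eCRF field. Sections 8.5 and 8.6 require accurate recording of administration, but the items listed in 6.2 do not name the side.
4. Reconcile the statement in 10.6 about placebo in the other leg with the one-leg injection in 4.1 and 8.2 before either contrast is interpreted.
5. Clarify the inter-subject terms in the Summary and 10.6.

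The cost is a few words of text and one eCRF check, with no new visits or procedures. The downside is the limited precision shown above, so the contrasts should stay descriptive.
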